### Rationale for Biomarkers selection

**microRNA:** Modulation of biological markers after treatment and the correlation of these findings with modification of lung nodules diameters will be investigated as secondary endpoints. In particular, we have recently identified serum circulating microRNA (miRNA) able to accurately predict the presence of lung cancer during early stages disease. The test was accurate enough to capture the onset of the disease in patients of whom serum samples were available before and after diagnosis of lung cancer by ld-CT. The same signature was also able to identify the premalignant GGO lesions among Cosmos 1 participants (unpublished data). In brief, we screened a group of 27 individuals with GGO lung nodules and applied the miRNA test. Twenty-four out of 27 were positives to the test (~89%). Furthermore, the average miRNA-test risk score of the GGO group was 12.5 while the average score of two other groups of individuals with solid nodules (N=25), or without nodules (N=25), were -2.2 and -4.4 respectively (p <0.0001; Student's t-test). This confirmed the validity of the miRNA-test to predict the presence of GGO lesions as well as early stages lung cancer, and suggest that active or passive release in the blood of specific miRNA species is already present in lung premalignant lesions.

The advantages of such a test compared to ld-CT are the potential for an easy applicability on a population-wide scale, the high potential for implementation of screening on a nation-wide scale, the absence of risks related to ionizing radiations, and the reduced costs

As regards the technical aspects we have developed a fully automatized procedure based on low-density qRT-PCR array that allows the screening of expression of ~800 different miRNA species and using less than 300µl of serum. This will give us the opportunity to test every known miRNA present in the serum and to perform an accurate analysis of their quantities.

We intend to apply the very same technology to identify serum miRNAs predictive of the effect of aspirin treatment in patients with GGO lung nodules.

**C-reactive Protein:** Inflammation has been hypothesized to increase the risk of cancer although data from epidemiologic study are sparse. Many inflammatory conditions are well-known cancer precursors (Barrett's esophagus, chronic gastritis, hepatitis, pancreatitis, and ulcerative colitis). So, early correction of inflammatory conditions by chemoprevention may be theoretically very useful. C-reactive protein (CRP), a member of the pentraxin family of proteins involved with pattern recognition in innate immunity, is the principal downstream mediator of the acute-phase response and is primarily derived via the interleukin 6-dependent hepatic biosynthesis. Moreover, ultrasensitive CRP (hs-CRP) is an known index of subclinical systemic inflammation associated with increased risk for cardiovascular events and diabetes. Elevated levels of hs-CRP have been linked to colon cancer development and a recent meta-analysis including 1,918 lung cancer cases points to its implication also with lung cancer risk.

Given our previous experience in measuring hs-CRP in subjects at higher risk for breast cancer, we are interested in investigating change in hs-CRP also in subjects at higher risk of lung cancer.

**Cotinine:** Measurement of cotinine, the nicotine metabolite, provides an accurate estimate of recent tobacco smoke exposure and are able to account for individual differences in smoking practices, such as depth of inhalation and how much each cigarette is smoked.

**Prostaglandin (PGEM):** Prostaglandin synthesis is driven by the two COX. Prostaglandin E2 is the most abundant prostanoid in the human body and it has been implicated in various tumorigenic processes and

induces proliferation by activating at least two signalling pathways: Ras–Erk and glycogen synthase kinase-3 $\beta$  (GSK3 $\beta$ )– $\beta$ -catenin in colon and lung cancer cells. Circulating prostaglandin E2 is rapidly cleared by a single passage through the lungs and measurement of the metabolites is necessary to provide a reliable estimate for its actual production.

**Leukotriene E4 (LTE4):** Leukotriene E4 is an urinary metabolite indicating activation of the lipoxygenase pathway. To perform urine analysis for LTE4, we will show relationship between acetyl-salicylic acid (ASA) and the LTE4 shunt in healthy smokers.

**Thromboxane B2 (TXB2):** Thromboxane B2 is a biologically inactive metabolite of Thromboxane A2, an arachidonate metabolite with potent platelet aggregation activity and prothrombotic properties, that is rapidly hydrolyzed to TXB2. TXB2 is thus a suitable markers for monitoring platelet function and assessment of aspirin compliance.

### 3. SUMMARY OF STUDY PLAN

We will conduct a double-blind placebo-controlled phase IIb study in which participants will be randomized to receive either Aspirin (100 mg/day) or placebo for 12 months.

A total of 128 subjects will be accrued (randomized to drug or placebo); 64 per arm in a 3.5 year time period.

Participants will be men and women, current or former smokers, with undetermined subsolid lung nodules detected at low dose screening CT scan (without contrast medium) running at the EIO and MDACC. In addition, we will include subjects undergoing CT outside the context of a screening program, providing a subsolid nodule confirmation by a CT scan. Participants will be given 100 mg Aspirin daily or placebo for 12 months.

The primary endpoint will be the shrinkage of GGO and partially solid lung nodules after one-year treatment per-subject analysis.

Secondary endpoints will be the modulation of biological markers after treatment and the correlation of these findings with modification of lung nodules diameters. In particular we will evaluate the effect of Aspirin on a signature of serum miRNA correlated to subsolid nodules. Other secondary endpoints will be the per-lesion analysis including the evaluation of lung nodule density before and after treatment and the number and size of non target lesions. Additional biomarkers will include the modulation of hs-CRP, the evaluation of urinary cotinine as marker of tobacco exposure and investigation of the potential effect of aspirin according to its concentration, the measurement of urinary prostaglandin metabolites (PGEM) and urine leukotriene E4 (LTE4) both normalized to urinary creatinine concentration. Serum concentration of thromboxane B2 (TXB2) will be determined as a measure of compliance. We will also evaluate the tolerability of Aspirin at dose of 100 mg/day.

Complete physical exam and safety lab tests will be performed at 0, 6 and 12 months. Phone contact will occur at month 1, 3, 9 and 13 (i.e, one month after treatment completion).

Biomarkers: blood and urine will be collected at 0, 6 and 12 months

Lung lesions will be measured with a CT scan at 0 and 12 months. Both standard dose and low dose CT scans are allowed provided that the same procedure is used at both time points.

Duration of study will be five years: 3.5 years of accrual, one year of treatment and 0.5 year for biomarkers measurement.

## 4. PARTICIPANT SELECTION

### 4.1 Inclusion Criteria

4.1.1 Asymptomatic current or former smokers (having stopped within the last 20 years). See Appendix D

4.1.2 Age  $\geq$  50 years (risk of lung cancer in subjects under 50 is low thus screening is not indicated by actual international guidelines).

4.1.3 Smoking history  $\geq$  20 pack/years; subjects must be included in an ongoing annual screening with low dose CT scan **or**

must have two consecutive CT outside the context of a screening program confirming subsolid nodules as per inclusion criteria number 4.1.4.

4.1.4 Subjects must have subsolid (non solid or partially solid) nodules with size between 4 and 10 mm with any Volume Doubling Time (VDT) not candidate to surgical excision **and/or**

subsolid (non solid or partially solid) nodule larger than 10 mm with VDT higher than 400 days and not candidate to surgical excision.

4.1.5 All nodules should be persistent at least after three months follow up with CT; a reduction up to 15% of the diameter of the largest target nodule from the previous CT scan is allowed

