## 8. CRITERIA FOR EVALUATION AND ENDPOINT DEFINITION

### 8.1 Primary Endpoint

For the purposes of the primary endpoint, only sub-solid (non-solid or partially solid) nodules will be assessed. Target lesions are defined as non solid or partially solid nodules persistent at least after 3 months follow up with standard or low dose CT scan, at least 4 mm in size. Non target lesions include solid nodules (larger than 3.5 mm), new lesions at baseline (e.g., that were not present on prior CT) or non-solid or partially solid nodules < 4mm in size.

The primary end-point will be the difference in sum of longest diameters of baseline target lesions in a person-specific analysis. New subsolid lesions identified during follow-up satisfying the same criteria for the definition of target lesion will also be included in the analysis.

It has been assumed a -0.2 mm average reduction of the sum of the longest diameter of all non-solid and partially-solid lesions at 12 months with respect to baseline in the placebo arm and an expected average reduction of -1.0 mm in the aspirin group.

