## 13.2 Randomization/Stratification

In order to keep at minimum the imbalance in treatments a stratified blocked randomization strategy will be used considering only the relevant prognostic factors. Subjects will be stratified according to screening vs non screening CT scan, gender, smoking habits (current versus former smokers) and nodule type (non solid versus partially solid nodules). A blocked randomization will be done within each stratum. Other possible prognostic factors are age, the number of lesions, their volume doubling time and their size but since there is no evidence that they affect the response probability they will be included just in a stratified analysis, not during the randomization process.

Justification of stratification:

Stratification by nodule type and smoking status is planned because both non solid type and active smoking are associated with the risk of developing lung malignancies and their natural history, while stratification by screening vs non screening CT scan, and gender are conservative. The effect of aspirin has been variable in men and women for the prevention of certain conditions.

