## 13.3 Accrual and Feasibility

A sample size of 128 patients (64 per arm) achieve 80% power to detect a difference of -0.8 mm between the null hypothesis that both groups average reduction is -0.2 mm and the alternative hypothesis that the average reduction of target nodules in the aspirin group is -1.0 mm, with estimated effect size of 0.5 (common standard deviations of 1.6 mm) and with a significance level (alpha) of 0.05 using a two-sided two-sample t-test. The average shrinkage in the placebo arm is derived from the Budesonide trial.

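### The 15% limit on pre-entry shrinkage covers only the largest nodule, while the primary endpoint sums all target nodules, so a regressing smaller nodule can add noise and cost power

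*Combined protocol and SAP*

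**What the plan says.** Section 4.1.5 has two parts. The first applies to every nodule: "All nodules should be persistent at least after three months follow up with CT". The second is the only numerical limit on pre-entry shrinkage, and it is tied to one nodule: "a reduction up to 15% of the diameter of the largest target nodule from the previous CT scan is allowed". Persistence is never defined by change in size.

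Section 8.1 then defines what is measured: "Target lesions are defined as non solid or partially solid nodules persistent at least after 3 months follow up with standard or low dose CT", with a minimum size of 4 mm. It sets no condition on earlier shrinkage. Subsolid nodules under 4 mm and lesions new at baseline are non-target. The endpoint runs over all targets: "The primary end-point will be the difference in sum of longest diameters of baseline target lesions in a person-specific analysis".

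Some shrinkage without aspirin is already planned for. Section 8.1 states: "It has been assumed a -0.2 mm average reduction of the sum of the longest diameter of all non-solid and partially-solid lesions at 12 months" in the placebo arm, and section 13.3 adds: "The average shrinkage in the placebo arm is derived from the Budesonide trial". Section 13.3 does not give the source of the SD of 1.6 mm.

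Section 13.2 comes closest to recognising nodule trajectory: "Other possible prognostic factors are age, the number of lesions, their volume doubling time and their size". It leaves these factors to a stratified analysis and keeps them out of the randomisation. The primary test in section 13.4 is a t-test with no covariate.

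**The concern.** The entry rule acts on one nodule and the endpoint on all of them. By limiting shrinkage of the largest nodule, the plan accepts that regression before entry matters, but the limit does not reach the other nodules in the sum.

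The planned difference between arms is 0.8 mm on a sum with an SD of 1.6 mm. One small nodule that resolves can move a participant's sum by several times that difference. If such nodules are present in both arms, the SD of the change is larger than planned and 64 per arm gives less than 80% power. Power is what is at stake here; the validity of the test is not.

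**Working it through.** **1. The plan's own figure.** Inputs from section 13.3: difference 0.8 mm, SD 1.6 mm, two-sided alpha 0.05, two-sample t-test, 64 per arm. The effect size is 0.8/1.6 = 0.5. The t-test needs 63.8 per arm for 80% power, so 64, and power at 64 per arm is 80.1%. The plan's sample size reproduces.

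**2. Does the text admit such a nodule?** Take a nodule stable at 9 mm and a second that went from 8 to 5 mm between the two CTs.
- Section 4.1.5: the 9 mm nodule is the largest on both scans and has not shrunk. The second is still present. The 15% limit does not apply to it, although it shrank by 3/8 = 37.5%.
- Section 8.1: the second is subsolid, persistent and at least 4 mm, so it is a target.
- If it then disappears, the sum falls by 5 mm. That is 5/0.8 = 6.25 times the planned difference and 5/1.6 = 3.1 SDs.

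**3. Effect on power (assumptions).** The documents give no rate, so assume that a share q of participants in each arm has one such nodule, that it loses s mm over the year whatever the treatment, and that the 1.6 mm SD does not already include this. Then

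SD = √(1.6² + q(1−q)s²),

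with the 0.8 mm difference unchanged.

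| q | s (mm) | q(1−q)s² | SD (mm) | Power, 64 per arm | Needed per arm for 80% | Added mean change, both arms (mm) |
|---|---|---|---|---|---|---|
| 5% | 2 | 0.19 | 1.66 | 77% | 69 | −0.10 |
| 5% | 3 | 0.43 | 1.73 | 74% | 75 | −0.15 |
| 10% | 2 | 0.36 | 1.71 | 75% | 73 | −0.20 |
| 10% | 3 | 0.81 | 1.84 | 69% | 84 | −0.30 |

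**4. Bias and type I error.** In simulation (20,000 trials; 10% or 20% of each arm with a nodule losing 4 mm), the between-arm difference stayed at about −0.80 mm. With no true effect, the rejection rate stayed near 5%.

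**5. Does adjusting for pre-entry change help or harm?** Let e be the SD of reading error in the sum on one scan. The error on the baseline scan enters the follow-up change with a minus sign and the pre-entry change with a plus sign. With no true pre-entry change, the squared correlation is e⁴/(2e² × 1.6²) = e²/5.12.
- e = 0.7 mm: 0.49/5.12 = 0.096; residual SD 1.6 × √0.904 = 1.52 mm; power 84%.
- e = 1.0 mm: 1/5.12 = 0.195; residual SD 1.6 × √0.805 = 1.44 mm; power 88% (87% in simulation).

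With resolving nodules (10% of participants, 3 mm lost before entry and 3 mm after), simulation of 6,000 trials gave 69% with and without adjustment at e = 0.7 mm and at e = 1.0 mm, and a rise from 68% to 76% at e = 0.3 mm. The two influences pull the covariate's slope in opposite directions and can cancel. Adjustment therefore costs essentially nothing and sometimes gains, but it does not always recover the lost power. The values of e are assumptions.

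**The case against.** **The text permits such nodules but does not show that they occur.** This stands. The histology in section 2.3 (19% nonspecific fibrosis or organizing pneumonia in one resected series, 4% focal scar in another) shows that some of these opacities are not neoplastic. It does not show that they were shrinking.

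**Safeguards already narrow the gap.** Every nodule must persist for at least three months, targets must be at least 4 mm, scans are re-reviewed and re-measured (section 4.4), and a senior radiologist and thoracic surgeon discuss cases at the IEO (section 7.6). A participant with a single target nodule is fully covered by the 15% limit. All of this is true, but none of it limits shrinkage of a second nodule.

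**The wording could be read more strictly.** Section 4.1.5 might grant a tolerance to the largest nodule alone, with none for the others. It also does not say which scan decides which nodule is largest. Both readings are open, but section 8.1 carries no such limit.

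**Some regression is already planned for.** The −0.2 mm placebo change may include it, and so may the SD. The 10%, 3 mm case alone adds −0.3 mm, more than the whole planned placebo change unless growth elsewhere offsets it. This is why the power figures are illustrations only.

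**Stronger readings.** A reader might infer a bias towards no effect. Regression shared by both arms does not produce one; only dilution, if aspirin cannot act on a resolving nodule, would shrink the effect, and nothing in the documents quantifies that. A reader might also push the assumptions further: 20% of participants losing 5 mm gives 42% power. That implies an extra mean change of 0.20 × 5 = 1.0 mm in both arms, five times the planned placebo change, and should not be relied on.

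**Conclusion.** The mismatch between sections 4.1.5 and 8.1 is real, and no other section closes it. A smaller nodule that is already regressing can be a target lesion, and its later regression then enters the primary sum in both arms. The consequence is extra variance and a possible loss of power, with type I error intact and no bias in the comparison.

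The loss cannot be sized from the documents. At 5-10% of participants and 2-3 mm it takes power from 80% to between 77% and 69%, provided the 1.6 mm SD does not already include such regression. If it does, the loss is smaller or absent. The plan's sample size arithmetic is correct on its own inputs. The change is worth making because it is cheap, not because harm has been shown.

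**What to change.** In section 13.4, pre-specify the primary comparison as a between-arm linear model of the 12-month change in the target-lesion sum. Adjust it for the baseline sum and for the change in that sum between the two qualifying CTs, expressed per month because the interval varies. A between-arm model also matches the two-sample comparison used for the sample size in section 13.3.

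Add a sensitivity analysis that leaves out target nodules that shrank by more than 15% before entry.

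Leave the target-lesion definition in section 8.1 as it is. Extending the 15% limit to every nodule is tempting, but 15% of a 4 mm nodule is 0.6 mm, which is within plausible reading error. Such a cut would remove stable small nodules and select on baseline measurement error. The sensitivity analysis shares this weakness, so it should remain secondary.

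**Cost.** No new scans: section 8.1 already requires each baseline target to have been seen on an earlier CT. The smaller target nodules must, however, be measured on that scan. It may have used a different scan protocol, because the same-procedure rule in sections 3 and 7.1 covers only the scans before and after treatment.

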4.1.6 All current smokers should accept to receive support for smoking cessation

4.1.7 ECOG performance status  $\leq$  1 (Karnofsky  $\geq$  70%; see Appendix A)

4.1.8 Participants must have normal organ and marrow function as defined below:

Leukocytes	$\geq$ 3,000/microliter
Absolute neutrophil count	$\geq$ 1,500/microliter
Platelets	$\geq$ 100,000/microliter
Total bilirubin	$\leq$ 2 $\times$ institutional ULN and/or history of Gilbert's syndrome
AST (SGOT)/ALT (SGPT)	$\leq$ 1.5 $\times$ institutional ULN
Serum creatinine	$\leq$ institutional ULN

4.1.9 The effects of Aspirin on the developing human fetus at the recommended therapeutic dose are unknown. For this reason and because acetyl salicylic acid (ASA) is known to be teratogenic, women of child-bearing potential (from first menstruation to 1 year after last menstruation) must agree to use adequate contraception (hormonal or barrier method of birth control; abstinence) prior to study entry and for the duration of study participation.

Should a woman become pregnant or suspect she is pregnant while participating in this study, she should inform her study physician immediately.

4.1.10 Ability to understand and the willingness to sign a written informed consent document.

4.1.11 Signed informed consent.

## 4.2 Exclusion Criteria

4.2.1 Subjects with chronic treatment (at least twice/week for more than 3 months) with Aspirin or other NSAIDs.

4.2.2 History of allergic reactions attributed to compounds of similar chemical or biological composition to aspirin, NSAIDs, COX2 inhibitors.

4.2.3 Invasive malignancy (with the exclusion of basal cell carcinoma or skin squamous cell carcinoma) diagnosed during the last 2 years before randomization; stage I-II invasive malignancies that were diagnosed more than 2 years prior to randomization and have been treated curatively are allowed as long as all treatment is finished at least 18 months prior to randomization.

4.2.4 History of therapeutic doses of anticoagulants including warfarin and low molecular weight Heparin (e.g. for prior deep venous thrombosis and pulmonary embolisms) in the preceding year.

4.2.5 Uncontrolled intercurrent illness including, but not limited to, ongoing or active infection, symptomatic congestive heart failure, unstable angina pectoris, cardiac arrhythmia, or psychiatric illness/social situations that would limit compliance with study requirements.

4.2.6 Pregnant women are excluded from this study because Aspirin is an agent with the potential for teratogenic or abortifacient effects. Because there is an unknown but potential risk for adverse events in nursing infants secondary to treatment of the mother with Aspirin, breastfeeding should be discontinued if the mother is treated with Aspirin.

4.2.7 Individual may not be receiving any other investigational agents, antiplatelet agents (e.g. aspirin, clopidogrel (plavix or others)), anticoagulants (e.g. heparin or heparinoids, coumadin, or others), metotrexate, lithium.

4.2.8 Participants with bleeding diathesis, history of gastric/duodenal ulcers in the last 5 years, NSAID-precipitated bronchospasm, patients unwilling or unable to limit alcohol consumption to i.e.  $\leq 3$  alcohol drinks a day.

4.2.9 Participants who in the opinion of the PI will be at higher risk of ASA-related complications.

4.2.10 Participants with known inability to adequately absorb oral medication.

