### 5.5 Concomitant Medications

Other NSAIDs or glucocorticosteroids should be avoided or limited. Any use of systemic or topic NSAIDs or glucocorticosteroids should be clearly documented (time, doses, routes, indications) and followed regularly.

If a participant requires pain relievers or antipyretics, the use of non-NSAIDs, e.g., acetaminophen, should be encouraged. It is not necessary to break the blind in most situations. A protonic pump inhibitor (PPI, omeprazole 20 mg/day tablet) will be added during the period of any NSAIDs or glucocorticosteroids treatment and will be stopped once NSAIDs or glucocorticosteroids are withdrawn.

Short courses of systemic NSAIDs or glucocorticosteroids (defined as up to 2 weeks at a time) are allowed. No more than 1 month total of off-protocol NSAIDs or glucocorticosteroids is allowed in a 6 months period. If it is anticipated that continuous NSAIDs or glucocorticosteroids will be needed or if more than 1 month of NSAIDs or glucocorticosteroids occurs during a 6 months period, the participant will stop study drug. However, since the participant will still undergo his/her yearly scan, they can still be assessed in an intent-to-treat analysis and thus do not come off the study. Non systemic glucocorticosteroids use is allowed without time restrictions.

All medications (prescription and over-the-counter), vitamin and mineral supplements, and/or herbs taken by the participant will be documented on the concomitant medication CRF and will include: 1) start and stop date, dose and route of administration, and indication. Medications taken for a procedure (e.g., biopsy) should also be included.

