### *Randomization:*

Participants will be assigned a randomization number once the following has been accomplished: eligibility has been verified at the site level, eligibility has been confirmed by the site PI, and eligibility CRF has been entered into the DMI web application. The randomization number will be generated by the database and assigned to the participant. Refer to Section 13.2 for details of randomization.

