## **8.3 Off-Agent Criteria**

Participants may stop taking study agent for the following reasons: completed the protocol-prescribed intervention, adverse event or serious adverse event, inadequate agent supply, noncompliance, concomitant medications, medical contraindication. Participants will continue to be followed, if possible, for safety reasons and in order to collect endpoint data according to the schedule of events. Subjects will not be replaced.

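### Section 4 does not exclude people on continuous systemic glucocorticosteroids, although section 5.5 would have them stop study drug as soon as they are randomised

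*Combined protocol and SAP*

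**What the plan says.** **Entry.** Criterion 4.2.1 excludes "Subjects with chronic treatment (at least twice/week for more than 3 months) with Aspirin or other NSAIDs". Criterion 4.2.7 lists other current medications that bar entry (investigational agents, antiplatelets including aspirin, anticoagulants, methotrexate, lithium). Neither names glucocorticosteroids, and no other item in 4.1 or 4.2 does. Criterion 4.2.9 gives a discretionary exclusion: "Participants who in the opinion of the PI will be at higher risk of ASA-related complications".

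**On study.** Section 5.5 handles NSAIDs and glucocorticosteroids together. Short courses are tolerated within limits. Then: "If it is anticipated that continuous NSAIDs or glucocorticosteroids will be needed or if more than 1 month of NSAIDs or glucocorticosteroids occurs" within six months, study drug stops. The rule is confined to systemic steroids by its closing sentence: "Non systemic glucocorticosteroids use is allowed without time restrictions". For participants who have been stopped, 5.5 says "they can still be assessed in an intent-to-treat analysis and thus do not come off the study". Section 8.3 adds: "Subjects will not be replaced".

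**Gatekeeping.** Under 6.8 a randomisation number is issued once eligibility has been verified at the site and "eligibility has been confirmed by the site PI, and eligibility CRF has been entered into the DMI web application".

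**Analysis and sample size.** Section 13.4 analyses randomised participants who took at least one dose. Section 13.3 plans 64 per arm for 80% power at a 0.8 mm difference, SD 1.6 mm, two-sided alpha 0.05.

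**The concern.** The NSAID half of the 5.5 stop rule has a counterpart at entry, in 4.2.1. The steroid half has none. For someone already on maintenance systemic steroids, continuous need is anticipated on the day of randomisation, so the plan as written admits the person and at once directs that study drug be stopped.

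Stopping drug while keeping follow-up is the right handling for a need that arises after randomisation. It gives no reason to enrol someone whose need is known beforehand, and the documents offer no rationale for doing so.

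Four things are at stake, all on a small scale:

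- One of 128 places is used by someone who cannot receive the intervention.
- The aspirin-placebo contrast is diluted if a dose is taken, or a participant is lost from the analysis set if not.
- Some participants may take aspirin with a systemic steroid, a combination that 5.5 itself treats as needing a proton pump inhibitor.
- The steroid may act on the endpoint: section 2.3 reports that inhaled budesonide affected non-solid nodules.

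**Working it through.** **Step 1. Set the two rules side by side.**

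| Treatment at screening | Barred by 4.1-4.2? | Meets the 5.5 stop rule at randomisation? |
|---|---|---|
| Chronic NSAID, at least twice weekly for over 3 months | Yes, 4.2.1 | Not relevant |
| Current aspirin | Yes, 4.2.7 | Not relevant |
| Non-systemic steroid | No | No, exempt in 5.5 |
| Short systemic course, completed | No | No |
| Continuous systemic steroid | **No named criterion** | **Yes** |

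Only the last row is inconsistent. A marginal neighbour is continuous non-aspirin NSAID use that began less than 3 months ago and cannot be switched. Section 5.5 already steers such people elsewhere: "If a participant requires pain relievers or antipyretics, the use of non-NSAIDs, e.g., acetaminophen, should be encouraged". It adds little to the point.

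**Step 2. Follow such a person through the plan.**

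- At least one dose taken, then stopped: kept in the intention-to-treat analysis (5.5, 13.4), and likely to fall below 80% of drug taken and so leave the efficacy analysis (13.4, 13.6).
- Stopped before any dose: outside the 13.4 analysis set. Section 13.8 describes undosed participants only as a possible exception to the main analysis.
- Either way, not replaced (8.3).

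**Step 3. Reproduce the planned power.** Inputs from 13.3: difference 0.8 mm, SD 1.6 mm, two-sided two-sample t-test, alpha 0.05.

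Effect size = 0.8 / 1.6 = 0.5. The exact t-test needs 63.77 per arm, which rounds up to 64 per arm and 128 in total, with power 80.1%. The plan's figure reproduces.

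**Step 4. Illustrate the loss.** The documents give no prevalence, so the counts below are assumptions.

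If k people per arm are dosed, stopped and retain no aspirin effect, with SD unchanged:

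difference = 0.8 × (1 − k/64), n = 64 per arm.

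If k per arm are stopped undosed: difference = 0.8, n = 64 − k per arm.

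| Assumed k per arm | Diluted difference | Power, diluted | Power, lost undosed |
|---|---|---|---|
| 0 | 0.8 mm | 80.1% | 80.1% |
| 1 | 0.7875 mm | 78.9% | 79.5% |
| 2 | 0.775 mm | 77.6% | 78.9% |

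Expressed as an assumed share of each arm, diluted power is 79.4% at 1% (0.792 mm), 76.0% at 5% (0.76 mm) and 71.4% at 10% (0.72 mm). The range follows from the assumed share and is not an estimate of what would happen.

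**The case against.** The strongest reply is that several checks already stand in the way. The investigator may exclude under 4.2.9, and 4.2.5 removes uncontrolled illness. Concomitant medications are recorded before randomisation (7.1). Section 10.2 asks about oral steroids by name on the day of the baseline miRNA draw. The site PI must confirm eligibility (6.8). Harm would need an investigator to randomise someone already known to have to stop. Moreover, 5.5 is a management rule for participants on study, and stopping drug, continuing follow-up and not replacing is ordinary intention-to-treat conduct.

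Much of this stands. The event should be uncommon, and non-replacement is not a fault in itself. But 4.2.9 turns on opinion about aspirin complications, 4.2.5 need not apply to someone stable on maintenance treatment, the medication questions only record use, and PI sign-off confirms listed criteria that do not include this one. Two sites following the plan faithfully could decide the same case differently.

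The power figures are also open to challenge: the counts are arbitrary, and the model treats steroids as inert on nodule size, which sits badly with the budesonide result in 2.3. That objection stands. The direction and size of any net effect are unknown.

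A reader might infer more than the text supports:

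- *That intermittent NSAID users enter already meeting the stop rule.* They do not. At two days a week, the one-month limit takes about 30 / 2 = 15 weeks to reach; at one day a week, 26 days in 26 weeks never reaches 30.
- *That the primary endpoint is lost for these people.* Section 5.5 keeps them on study, and the 12-month CT is still planned.
- *That the trial suffers a material or bounded power loss.* Without a prevalence, the documents support neither.

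**Conclusion.** The point holds as a mismatch between two stated rules. Sections 4.1-4.2 permit entry of a person on continuous systemic glucocorticosteroids, and 5.5 directs that the same person stop study drug at once. The existing safeguards lower the chance of this but do not require exclusion.

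The weight is minor. The textual omission is certain; how many people it would affect, and whether results would change, cannot be judged from the documents. The one-per-arm illustration, a fall of 1.2 percentage points (80.1 − 78.9), assumes one such person in each arm, no retained aspirin effect, an unchanged SD and no direct steroid effect on nodules. It shows scale only and is neither an estimate nor an upper limit. The sample size of 128 is not in question.

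**What to change.** Leave 4.2.1 as it stands and add one exclusion to 4.2: *Current or anticipated continuous use of systemic glucocorticosteroids (or NSAIDs) that would meet the section 5.5 stop rule at randomisation.* State that non-systemic steroids and completed short courses remain allowed.

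Add one line to the eligibility CRF, checked against the concomitant medication record that the schedule of events already requires before treatment. Because 6.8 makes entry of that CRF a condition for issuing the randomisation number, the check falls at the right moment.

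The cost is one criterion and one CRF line, with no new data collection and no change to the sample size, endpoint or analysis. A few candidates are lost who could not have stayed on study drug.
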